4.1 Type/Design of Trial

This will be a phase 2, multicenter, randomized, double-blind, placebo-controlled trial to assess the efficacy, safety, and tolerability of centanafadine SR tablets for the treatment of adult subjects with BED. Subjects with a primary clinical diagnosis of moderate to severe BED based on the DSM-5⁷ diagnosis criteria and confirmed by the SCID-5-CT will be eligible for enrollment. The trial will consist of a screening period of up to 28 days that includes completion of a binge eating diary for at least 14 days (that shows at least 3 binge eating days in each week during the previous 14 days of a subject's screening period as reviewed at baseline [minimum screening period is 2 weeks]), a baseline visit, an 8-week (56-day) double-blind treatment period, and a 7-day safety follow-up period. All baseline assessments will be conducted prior to first dose of IMP.

Eligible subjects will be randomized 1:1:1 at baseline to receive 1 of 2 doses of centanafadine SR or placebo daily for 8 weeks. The doses of centanafadine SR that will be assessed in adult subjects during this trial were selected based on the efficacious and safe doses in the adult ADHD phase 2 and 3 trials.

All subjects who terminate early will be required to participate in a 7-day safety follow-up period, which will consist of telephone contact 7 (+ 2) days after the last dose of investigational medicinal product (IMP). For subjects who early terminate, they will be instructed to refrain from using prohibited concomitant medications, including BED treatments, until after the safety follow-up visit.

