6.1 Trial Treatments Administered

Eligible subjects will be randomized 1:1:1 at baseline to receive 1 of 2 doses of centanafadine SR or placebo daily for 8 weeks:

- High dose centanafadine: 400 mg centanafadine SR oral tablets TDD (2 × 100 mg BID, approximately 4 6 hours apart)
- Low dose centanafadine: 200 mg centanafadine SR oral tablets TDD $(1 \times 100 \text{ mg}) + 1 \text{ placebo oral tablet (BID, approximately 4 6 hours apart)}$
- Placebo: 2 placebo oral tablets (BID, approximately 4 6 hours apart)

Neither the investigator nor the subject will be aware of the treatment assignment after randomization. IMP will be dispensed at the baseline visit and the first dose of IMP will be taken on the morning of Day 1, when the subjects will be home. A telephone call will be placed from site to subject to confirm dosing. The date and time of the first dose will be recorded.

All doses of centanafadine SR and matching placebo should be taken orally BID (with up to 240 mL of water). Doses should be taken at approximately the same time each day, with the first dose taken in the morning and the second dose taken 4 to 6 hours after the morning dose is administered. All doses can be administered without regard to meals.

If a subject forgets to take their morning dose at their normal dosing time, the subject should take the dose as soon as they remember that same day. If a subject forgets to take their second dose and 6 hours have elapsed since the time of the morning dose, they should skip the dose and resume dosing the next day. If a subject does not remember to take a missed dose on the same day it is missed, the subject should skip that dose and resume the normal dosing schedule for the following dose. Subjects should not take more than 2 doses in one day.

For information regarding the dose regimen and treatment period(s), including any follow-up period(s) for each treatment group/arm of the trial, see Section 4.1.

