An AE is defined as any untoward medical occurrence in a clinical trial subject administered an IMP and which does not necessarily have a causal relationship with this treatment. Adverse events would not include information recorded as medical history at

screening for pre-planned procedures for which the underlying condition was known and no worsening occurred. An adverse reaction is any untoward and unintended response to an IMP related to any dose administered.

A suspected adverse reaction is any AE for which there is a reasonable possibility that the IMP caused the AE. For the purpose of Investigational New Drug (IND) safety reporting, "reasonable possibility" means there is evidence to suggest a causal relationship between the IMP and the AE. Suspected adverse reaction implies a lesser degree of certainty about causality.

Treatment-emergent AEs (TEAEs) are defined as AEs with an onset date on or after the start of double-blind treatment. In more detail, TEAEs are all AEs which started after the start of double-blind IMP treatment; or if the event was continuous from baseline and was worsening, serious, IMP related, or resulted in death, discontinuation, interruption, or reduction of IMP.

An SAE includes any event that results in any of the following outcomes:

- Death
- Life-threatening; ie, the subject was, in the opinion of the investigator, at immediate risk of death from the event as it occurred. It does not include an event that, had it occurred in a more severe form, might have caused death.
- Persistent or significant incapacity/disability or substantial disruption of the ability to conduct normal life functions.
- Requires inpatient hospitalization or prolongs hospitalization.
 - Hospitalization itself should not be reported as an SAE; whenever possible the reason for the hospitalization should be reported.
 - Hospitalizations or prolonged hospitalizations for social admissions (ie, those required for reasons of convenience or other nonmedical need) are not considered SAEs.
 - Prescheduled hospitalization to address a condition that has existed prior to the signing of the ICF should not be considered an SAE.
- Congenital anomaly/birth defect.

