8.8.2 Eliciting and Reporting Adverse Events

The investigator will regularly assess subjects for the occurrence of AEs. To avoid bias in eliciting AEs, subjects should be asked the nonleading question: "How have you felt since your last visit?" All AEs (serious and nonserious) reported by the subject must be recorded on the source documents and eCRF provided by the sponsor. Adverse event collection will begin after a subject signs the ICF, and will continue until the subject's last scheduled contact unless the AE must be followed further (see Section 8.8.9). All AEs must be reported after subject informed consent has been obtained, including screening failures due to AEs, irrespective of IMP administration.

Medical terminology should be used for AE reporting. Adverse events should be reported as a single unifying diagnosis whenever possible or, in the absence of a unifying diagnosis, as individual signs or symptoms.

Exacerbation or disease progression should be reported as an AE only if there are unusual or severe clinical features that were not present, or experienced earlier, or not expected based on the course of the condition. In addition, the sponsor must be notified immediately by telephone, fax, or e-mail of any IREs according to the procedure outlined below, in Section 8.8.3. Special attention should be paid to recording hospitalization and concomitant medications.

The adverse event, start date, end date, seriousness, severity, relationship to trial treatment (IMP causality), action taken with trial treatment, and outcome will be recorded on the source documents and in the eCRF.

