5.1 Baseline and Last Visit Definition

In general, baseline is defined as the last available measurement prior to the first dose of IMP in the double-blind treatment period. Last visit is defined as the last available measurement by completion or termination in the double-blind treatment period.

However, baseline for binge eating days per week is the number of confirmed binge eating days divided by the number of non-missing diary days within 14 days prior to randomization, and multiplied by 7. Similarly, baseline for number of binge episodes per week is the number of confirmed binge episodes (by principal investigator) divided by the number of non-missing diary days within 14 days prior to randomization, multiplied by 7.

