9.2 Adverse Events

All AEs will be coded by system organ class (SOC) and Medical Dictionary for Regulatory Activities (MedDRA) Preferred Term (PT). The incidence of the following events will be summarized by treatment group:

- a) Treatment-emergent AEs (TEAEs)
- b) TEAEs by severity
- c) TEAEs potentially causally related to the IMP
- d) TEAEs with an outcome of death
- e) Serious TEAEs
- f) TEAEs leading to discontinuation of the IMP
- g) Treatment-emergent Adverse Events of Special Interest (AESI) related to Rash
- h) TEAEs related to Abuse
- i) TEAEs involving Medication Handling Irregularities (MHI)

AEs will be classified by primary SOC and PT according to MedDRA. AEs that are gender-specific, e.g., ovarian cancer, will have their incidence rates evaluated for the specific gender. TEAEs are all adverse events which started after start of IMP; or if the event was continuous from end of the single-blind placebo run-in period and was worsening, serious, study drug related, or resulted in death, discontinuation, interruption, or reduction of study therapy. Adverse events occurring up to 30 days after the last day of double-blind dosing will be included in the summary tables.

Incidence of TEAEs will be summarized by treatment group. Incidence of TEAE of at least 5% in either centanafadine group and greater than placebo will be provided by treatment group, SOC and MedDRA PT.

AESI related to rash will be selected from AESI worksheet and AE CRF. TEAEs related to abuse will be searched based on specified MedDRA PTs. TEAEs involving MHI will be selected from Events Subject to Additional Monitoring (ESAM) form and AE CRF.

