- CT-6.1.6 Columbia-Suicide Severity Rating Scale Listing of Treatment Emergent Suicidal Ideation (Safety Analysis Set)
- CT-6.1.7 Columbia-Suicide Severity Rating Scale Listing of Treatment Emergent Serious Suicidal Ideation (Safety Analysis Set)
- CT-6.1.8 Columbia-Suicide Severity Rating Scale Listing of Worsening Suicidal Ideation (Safety Analysis Set)
- CT-6.2 Summary of Change from Baseline in Hamilton Anxiety Rating Scale Total Score (Safety Analysis Set)
- CT-6.3 Summary of Change from Baseline in Montgomery-Asberg Depression Rating Scale Total Score (Safety Analysis Set)
- CT-6.4 Summary of Study Medication Withdrawal Questionnaire (SMWQ) Total Score (Safety Analysis Set)
- CT-7.1 Extent of Exposure (Safety Analysis Set)
- CT-7.2 Number and Percentage of Subjects Receiving Study Medication and Mean and Range of Average Daily Dose (Safety Analysis Set)
- CT-8.1.1 Adverse Events (All Causalities) (Safety Analysis Set)
- CT-8.1.2 Adverse Events During the Single-Blind Placebo Run-in Period (All Causalities) (Safety Analysis Set)
- CT-8.2.1 Incidence of Treatment-Emergent Adverse Events by System Organ Class and MedDRA Preferred Term (Safety Analysis Set)
- CT-8.2.2 Incidence of Treatment-Emergent Adverse Events by System Organ Class, MedDRA Preferred Term and Severity (Safety Analysis Set)

- CT-8.2.3 Incidence of Treatment-Emergent Adverse Events of at Least 5% in Any Centanafadine Group and Greater Than Placebo by System Organ Class and MedDRA Preferred Term (Safety Analysis Set)
- CT-8.2.4 Incidence of Non-Serious Treatment-Emergent Adverse Events of at Least 5% in Any Centanafadine Group and Greater Than Placebo by System Organ Class and MedDRA Preferred Term (Safety Analysis Set)
- CT-8.2.5 Incidence of TREATMENT-EMERGENT ADVERSE Events of at Least 2% in Any Centanafadine Group and Greater Than Placebo by System Organ Class and MedDRA Preferred Term (Safety Analysis Set)
- CT-8.2.6 Incidence and Occurrence (Number of Events) of Serious Treatment-Emergent Adverse Events by System Organ Class and MedDRA Preferred Term (Safety Analysis Set)
- CT-8.2.7 Incidence and Occurrence (Number of Events) of Potentially Drug-Related Serious Treatment-Emergent Adverse Events by System Organ Class and MedDRA Preferred Term (Safety Analysis Set)
- CT-8.2.8 Incidence and Occurrence (Number of Events) of Non-Serious Treatment-Emergent Adverse Events by System Organ Class and MedDRA Preferred Term (Safety Analysis Set)

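### SAP 9.2 ties the continuing-event part of the TEAE definition to a single-blind placebo run-in that this trial does not have; Protocol 8.8.1 ties it to baseline

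*SAP*

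**What the plan says.** SAP 9.2 defines a TEAE in two parts. The first covers events that start once IMP has started. The second covers events already present, and applies "if the event was continuous from end of the single-blind placebo run-in period and was worsening, serious, study drug related, or resulted in death"; the sentence then adds discontinuation, interruption or reduction of therapy.

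Protocol 8.8.1 has the same two parts, but its second part applies "if the event was continuous from baseline and was worsening, serious, IMP related, or resulted in death, discontinuation, interruption, or reduction of IMP".

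The design has no run-in. Protocol 4.1 describes up to 28 days of screening, then "a baseline visit, an 8-week (56-day) double-blind treatment period, and a 7-day safety follow-up period", and SAP 3.1 gives the same sequence. Protocol 6.1 states that "IMP will be dispensed at the baseline visit and the first dose of IMP will be taken on the morning of Day 1". SAP 5.1 follows this: in general, "baseline is defined as the last available measurement prior to the first dose of IMP in the double-blind treatment period".

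AEs are nevertheless recorded before dosing. Under Protocol 8.8.2, "Adverse event collection will begin after a subject signs the ICF, and will continue until the subject's last scheduled contact".

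The run-in appears once more, in SAP Appendix 4, where the title of table CT-8.1.2 begins "Adverse Events During the Single-Blind Placebo Run-in Period (All Causalities) (Safety Analysis Set".

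SAP 1 says that the plan agrees with protocol amendment 2. SAP 15 lists one departure, the removal of trial center from the lipid ANCOVA. It does not mention the TEAE definition.

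**The concern.** No event can be continuous from the end of a period that never took place. Taken at its word, the second part of the SAP definition therefore selects nothing, and only events with onset after the start of IMP count as TEAEs. The protocol means to count more: an AE that starts in screening and then worsens, becomes serious, is judged related, or leads to death, discontinuation, interruption or reduction.

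TEAE incidence is a main summary for the trial's secondary (safety) objective, and the SAP is where the analysis rules are fixed. Whoever programs the tables must either override the SAP text without a record or drop the second part. SAP 9.2 also applies a reporting cut-off: "Incidence of TEAE of at least 5% in either centanafadine group and greater than placebo will be provided by treatment group". With about 42 subjects per arm, one subject can decide whether a term meets it.

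**Working it through.** The plan states no figure to reproduce. The check is a comparison of text, followed by simple arithmetic on size.

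**Step 1. The two definitions side by side.**

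| Element | Protocol 8.8.1 | SAP 9.2 |
|---|---|---|
| New events | onset after double-blind IMP starts | onset after IMP starts |
| Continuing events counted from | baseline | end of single-blind placebo run-in |
| Further conditions | worsening, serious, related, or one of the listed outcomes | the same |

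Only the reference point for continuing events differs.

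**Step 2. Is there a run-in anywhere?** Protocol 1.1 and 4.1 and SAP 3.1 name screening, baseline, double-blind treatment and safety follow-up. The schedule of assessments (Protocol Table 1.3-1) shows IMP first dispensed at the baseline visit and first taken on Day 1. The design figure was not available to me, but its legend explains only the number of subjects, randomization and telephone visits. The run-in is mentioned in two places, SAP 9.2 and the title of CT-8.1.2, and nowhere in the protocol.

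**Step 3. Which events are exposed?** An event is affected only if all of the following hold:
- it starts between consent and first dose;
- it is still present at first dose;
- it then meets one of the further conditions;
- it is not entered again as a new AE.

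On the last point, the nearest text is Protocol 8.8.2, which lets an exacerbation be reported as an AE in limited circumstances. It does not say whether a worsening AE gets a new record, so re-recording cannot be assumed.

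**Step 4. Size per subject.** Input: 42 planned per arm (Protocol 1.1, SAP 3.3). The real denominator is the Safety Analysis Set.
- Largest effect on one row: 1/42 = 0.0238, or 2.4 percentage points.
- Smallest effect: 0, if the subject has another TEAE counted in that row.

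**Step 5. The 5% cut-off.** 0.05 × 42 = 2.1, so a term needs 3 subjects.
- 3/42 = 7.1%: meets the cut-off.
- 2/42 = 4.8%: does not.
- With 40 in an arm, 2/40 = 5.0% meets it and 1/40 = 2.5% does not.

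In each case one omitted subject can decide whether a term appears in CT-8.2.3 and CF-3. An omission on placebo can work the other way. With 3/42 on both centanafadine and placebo, the term is not greater than placebo and is not shown; if one placebo event is omitted, it becomes 7.1% against 4.8% and is shown.

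**Step 6. Where the events would still be seen.** The title of CT-8.2.1 sets no frequency cut-off, so a term at 2/42 stays there. CT-8.2.5 uses 2%, and 4.8% passes that if it exceeds placebo. The omitted event itself would be in the all-AE table CT-8.1.1 and listing AE-1. Deaths, SAEs and AEs leading to discontinuation would be in CT-9.1 to CT-9.3, whose titles are not limited to TEAEs.

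**The case against.** The best defense is that the intent is plain. The SAP keeps every condition attached to continuing events, so it clearly means to include them. SAP 1 claims agreement with the protocol and SAP 15 declares no change, so a sensible analyst would use the protocol's baseline. On this view the run-in is wording carried over from elsewhere, and few events are involved.

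Much of this stands. The meaning can be recovered from Protocol 8.8.1 and SAP 5.1, most TEAEs fall under the first part and are untouched, and the documents give no count of exposed events. It does not make the stated rule right. A prespecified safety definition should not depend on the programmer noticing that it cannot be applied, and the second mention in CT-8.1.2 shows that this is not an isolated slip.

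A reader might go further in four ways that the documents do not support:
- **A count of affected tables.** Appendix 4 has 22 tables titled for treatment-emergent events (8 under CT-8.2 and 2 each under CT-8.3 to CT-8.9). How many would change cannot be derived. Several present the same events again by severity or seriousness. The drug-related tables cannot be set aside on the ground that causality needs a temporal link, because relatedness is itself a qualifying condition in both definitions.
- **A term vanishing from the report.** It would leave the 5% displays only; Step 6 shows where it remains.
- **A bias for or against centanafadine.** Omissions can occur in any arm, and nothing in the documents gives a direction.
- **A need to change the onset boundary too.** Protocol 8.8.1 words the boundary in two ways, and SAP 9.2 already matches the more detailed sentence. That matter is separate from the run-in.

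**Conclusion.** The point holds as an inconsistency in a stated analysis rule. SAP 9.2 cannot be applied as written to AEs already present at first dose, and it conflicts with Protocol 8.8.1 without a declared change.

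The practical effect is probably small. It is bounded by 2.4 points per affected subject per row at 42 per arm, with a possible change in what passes the 5% cut-off. The bound assumes the planned arm size. The 5% example assumes a term with exactly 3 subjects, one of them with an omitted event; this is an illustration, since the documents give no expected frequency. The loss also assumes that a worsening AE is not entered as a new one. No efficacy result, sample size or error rate is involved.

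**What to change.** Change the SAP only:
- In 9.2, replace the reference to the end of the single-blind placebo run-in with baseline, as in Protocol 8.8.1.
- In Appendix 4, delete CT-8.1.2 or retitle it as AEs with onset before the first dose of IMP.

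The cost is one phrase and one table title. No new data are needed. No protocol amendment is needed either, because Protocol 8.8.1 already counts from baseline and stays as it is.

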8.8.5 Adverse Events of Special Interest

Newly acquired skin eruptions that are non-traumatic will be considered AESIs. These may include, but are not limited to eruptions such as skin rashes, skin irritations, skin reactions, or acneiform lesions. This does not include localized contact irritation at ECG lead sites due to application/removal of lead adhesive.

Refer to the separate Rash/Skin Eruption AESI Workup Instructions for complete details, including reporting forms, on extra measures that must be performed to characterize any skin AESI of a newly acquired skin eruption that is non-traumatic.

All AESIs should be reported as IREs (see Section 8.8.3).

8.8.6 Abuse Potential Monitoring Process, Events Subject to Additional Monitoring, and Medication Handling Irregularities

An Abuse Potential Monitoring Process (APMP) will be in place and will be shared with each site. A key objective of the APMP is to monitor for instances of abuse or diversion of the trial medication and other psychoactive substances. In addition to monitoring for irregularities in medication handling, AEs that may be suggestive of a developing abuse issue will also receive special attention. As part of the APMP, MHIs must be reported, and AEs related to abuse potential and AEs involving MHIs must be reported as an ESAM with detailed narratives.

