Investigators and site staff at each trial site will be trained on reporting potentially abuse related AEs (eg, recording a description of the event in the subject's own words in the source documents as well as the eCRF, in addition to the clinical term, and to be aware that a subject's report may encompass more than one event and that these should be recorded separately). The investigators will be provided with examples of potentially abuse-related AEs, and trained on how to handle such events (eg, additional monitoring). While the investigators will be provided with examples of AE terms as a guide during trial conduct, the analysis of potentially abuse-related AEs will be based on a search of all Medical Dictionary for Regulatory Activities (MedDRA) preferred terms, all verbatim terms, and any open text fields within the AE data to identify text strings suggestive of abuse potential, in line with the 2017 FDA guidance (Assessment of Abuse Potential of Drugs). Refer to the separate APMP documentation for complete details on MHIs and ESAMs, including documenting and reporting procedures, examples of potentially abuse related AE terms that meet the criteria for ESAM reporting, and guidance for the training of investigators and trial site staff.

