9.6	Electrocardiogram Data	27
9.7	Suicidality	28
9.8	Other Safety Data	29
10 R	ules for Scoring	29
10.1	Clinical Global Impression - Severity	29
10.2	Clinical Global Impression - Change	29
10.3	Yale-Brown Obsessive-Compulsive Scale Modified for Binge Eating	30
10.4	Eating Disorder Examination Questionnaire 7-Item Version	30
10.5	Patient Global Impression - Severity	3(

Protocol 405-201-00056 Statistical Analysis Plan

10.6	Patient Global Impression - Change	30
10.7	36-Item Short-Form Health Survey	30
10.8	Hamilton Anxiety Rating Scale	31
10.9	Montgomery-Asberg Depression Rating Scale	31
10.10	Study Medication Withdrawal Questionnaire	31
10.11	Columbia-Suicide Severity Rating Scale (C-SSRS)	31
11	Pharmacokinetic Analyses	32
12	Pharmacodynamic Analyses	32
13	Pharmacogenomic Analyses	32
14	Interim Analysis	32
15	Changes in the Planned Analyses	32
16	References	

List of In-text Figures

Figure 3.1-1	Twich Degion	Schematic 9
rigure 5.1-1	Trial Design	Schematic
1 15010 2.1 1	TITAL DUBISH	

List of In-text Tables

Table 5.2-1	Mapped Trial Week Windows for Counting Days or	
	Episodes of Binge Eating	12
Table 5.2-2	Mapped Trial Week Windows for Other Efficacy Analysis	13
Table 9.6-1	Categorical Change Criteria in QT/QTc Parameters	28

List of Appendices

Appendix 1	Criteria for Identifying Vital Signs and Weight of Potential Clinical Relevance	34
Appendix 2	Criteria for Identifying Laboratory Values of Potential Clinical Relevance	35
Appendix 3	Criteria for Identifying ECG Measurements of Potential Clinical Relevance	36
Appendix 4	List of Proposed Summary Tables	37
Appendix 5	Proposed Subjects Data Listing	43

1 Introduction

This statistical analysis plan (SAP) describes the statistical methodology and data analysis algorithms and conventions to be applied for statistical analysis and reporting of data collected under the clinical protocol 405-201-00056. All amendments to the protocol are taken into consideration in developing the SAP, which is consistent with latest version of protocol amendment 2 dated on 24 Jan 2022.

2 Trial Objectives

Primary objective is to assess the efficacy of 2 doses of centanafadine sustained release (SR) (ie, 200 and 400 mg total daily dose [TDD]) compared with placebo in adults with moderate to severe Binge Eating Disorder (BED).

[figure not shown]
Secondary objective is to assess the safety and tolerability of centanafadine SR tablets administered daily (200 and 400 mg TDD) in the treatment of subjects with BED.

3 Trial Design

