9.8 Other Safety Data

Change from baseline in HAM-A total score, MADRS total score will be summarized by treatment group in descriptive statistics. SMWQ total score will be summarized by treatment group.

Classification of MHIs and Classification of Events Reported as findings in ESAM form will be summarized in frequencies and proportion by treatment group.

10 Rules for Scoring

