10.11 Columbia-Suicide Severity Rating Scale (C-SSRS)

Suicidality will be monitored during the trial using the C-SSRS. The C-SSRS is a semistructured interview that captures the occurrence, severity, and frequency of suiciderelated thoughts and behaviors during the assessment period. The interview includes definitions and suggested questions to solicit the type of information needed to determine if a suicide-related thought or behavior has occurred.

The C-SSRS has a "Screening/Baseline" version, which will be completed at screening and a "Since Last Visit" version that will be completed at all scheduled visits (including the ET visit, if applicable). There are a maximum of 19 items to be completed: 7

required, 10 potential additional items if there is a positive response to a required item, and 2 items for suicide/suicide behavior present during the interview. The C-SSRS uses dichotomous scales (i.e., yes or no), Likert scales, and text or narrative to further describe the thoughts or behaviors.

11 Pharmacokinetic Analyses

Sparse PK samples will be evaluated to confirm compliance with dosing. Concentrations will be listed in the bioanalytical report.

12 Pharmacodynamic Analyses

No pharmacogenomic analyses is planned.

13 Pharmacogenomic Analyses

No pharmacogenomic analyses is planned.

14 Interim Analysis

No interim analyses is planned.

15 Changes in the Planned Analyses

Trial center will not be included in ANCOVA model for analyses of change from baseline in fasting triglycerides and total cholesterol at Week 8/ET.

16 References

- 3. Little RJA. Pattern-mixture models for multivariate incomplete data. J Am Stat Assoc. 1993; 88:125-34.
- 4. Little RJA. Modeling the drop-out mechanism in repeated measures studies. J Am Stat Assoc. 1995; 90:1112-21.

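### SAP Section 9.2 finds abuse-related TEAEs from specified preferred terms only, where Protocol Section 8.8.6 requires a search of all preferred terms, verbatim terms and open text, and the change is not declared

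*SAP*

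**What the plan says.** Protocol Section 8.8.6 sets the method for analysing potentially abuse-related AEs. Sites receive example terms to guide them during the trial, but the analysis itself "will be based on a search of all Medical Dictionary for Regulatory Activities (MedDRA) preferred terms, all verbatim terms, and any open text fields" in the AE data, "to identify text strings suggestive of abuse potential, in line with the 2017 FDA guidance". The same section requires that "AEs related to abuse potential and AEs involving MHIs must be reported as an ESAM with detailed narratives".

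SAP Section 9.2 describes the selection in one sentence: "TEAEs related to abuse will be searched based on specified MedDRA PTs". Verbatim terms and open text are not mentioned. Among the neighbouring categories, rash events are taken from the AESI worksheet and the AE CRF, and "TEAEs involving MHI will be selected from Events Subject to Additional Monitoring (ESAM) form and AE CRF".

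On agreement with the protocol, SAP Section 1 says that the protocol amendments were taken into account in the SAP, "which is consistent with latest version of protocol amendment 2 dated on 24 Jan 2022". SAP Section 15, which lists changes to the planned analyses, has a single entry: "Trial center will not be included in ANCOVA model for analyses of change from baseline in fasting triglycerides and total cholesterol at Week 8/ET".

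**The concern.** The protocol separates two uses of abuse-related terms: examples that help sites recognise events, and a full text-string search that decides what is analysed. The SAP replaces that search with a selection on specified preferred terms. This is a different method, and a reader of the SAP is told that nothing of the kind has changed.

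Abuse-related AEs are a named safety endpoint in Protocol Section 3. Protocol Section 4.2 argues that centanafadine may carry a lower abuse potential than stimulants, with possible consequences for scheduling. Under Section 8.8.6, sites are trained to record the subject's own description as well as the clinical term. A selection on preferred terms alone makes no use of that text. If it misses events, the abuse-related counts are too low in whichever arm they occurred.

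**Working it through.** There is no stated figure to reproduce, so the check is mainly a comparison of texts.

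| Item | Protocol 8.8.6 | SAP 9.2 |
|---|---|---|
| Preferred terms | all | specified terms |
| Verbatim terms | all | not named |
| Open text fields in AE data | any | not named |
| Role of predefined terms | examples to guide sites | basis of the selection |

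1. **Sources.** The protocol names 3 and the SAP names 1, in restricted form, so 3 − 1 = 2 are not named.

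2. **Can the selection be reproduced from the SAP?** No. The five appendices cover vital signs and weight, laboratory values, ECG, summary tables and data listings. None holds a list of abuse-related terms and Section 9.2 cites none. A list may exist in a document outside the two available here, but even a complete list of preferred terms would not restore the verbatim and open-text search.

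3. **Is the change declared?** No. Section 15 contains only the lipid ANCOVA item.

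4. **Which outputs are affected?** CT-8.8.1 (incidence), CT-8.8.2 (incidence by severity) and CT-9.5 (listing) report TEAEs related to abuse, so under SAP Section 9.2 they rest on this selection.

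5. **Where would a missed event still appear?** In CT-8.2.1, with all other TEAEs, and in listing AE-1, but without being identified as abuse-related. If the site flagged it, it would also enter CT-15, because SAP Section 9.8 says that "Classification of MHIs and Classification of Events Reported as findings in ESAM form will be summarized in frequencies and proportion by treatment group". That is a separate table and does not feed CT-8.8.1, CT-8.8.2 or CT-9.5.

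6. **Size per missed subject** (100 × 1/n percentage points):
   - n = 42, the planned number randomised per arm, taken as the Safety Analysis Set: 1/42 = 2.4 points in that arm.
   - n = 38, as an illustration of a smaller arm: 1/38 = 2.6 points.
   - n = 126, all arms together: 1/126 = 0.8 points.

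7. **Number missed.** The documents give no expected count or rate of abuse-related AEs, so this cannot be calculated. The lower bound is zero, reached if the term list is broad enough.

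**The case against.** The strongest reply is that SAP Section 9.2 does not say only preferred terms will be used. The specified terms might be the product of the wider search, or come from the separate abuse-potential monitoring documentation that Section 8.8.6 cites. That is possible, but the SAP does not say so. If it is what is meant, the SAP still needs a sentence to state it.

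A second reply is that abuse potential is covered elsewhere. Protocol Section 8.7 assesses it through active monitoring of ESAMs, SAP Section 9.8 and CT-15 summarise those forms, and every TEAE is in the general tables. This narrows the gap: an event drops out of all abuse-specific reporting only if its preferred term is unlisted and the site also did not flag it. It does not complete CT-8.8.1, CT-8.8.2 or CT-9.5, and CT-15 depends on the site recognising the event.

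Third, Protocol Section 9.4.2.1 does not list an abuse-related summary, and the search rule sits in a monitoring section, so the mismatch may be a drafting omission. That may explain how it arose. It leaves Section 8.8.6 as the protocol's statement of how these events are to be analysed.

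Some points on the other side stand. The 38 per arm is the evaluable number behind the efficacy power calculation, not a Safety Analysis Set size, so the 2.6-point figure is illustrative only. The protocol does not require the abuse tables to be selected from the ESAM form, so the contrast with MHI events shows uneven treatment within the SAP and is not a further breach. A text search also needs its strings written down, or it is no more reproducible than an unlisted set of terms.

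**Conclusion.** The concern holds. Read as written, SAP Section 9.2 departs from Protocol Section 8.8.6 without saying so, and the abuse-TEAE tables and listing could be incomplete. The mismatch itself is certain from the texts. Its effect on the counts is unknown and may be nil.

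The per-subject size of 2.4 percentage points assumes 42 subjects per arm in the Safety Analysis Set. The same search would apply in all arms, so no direction of bias in the centanafadine–placebo comparison is claimed. The matter is confined to a descriptive safety summary. It should be fixed because the endpoint is named in the protocol and the correction is cheap.

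**What to change.** Rewrite the sentence in SAP Section 9.2 so that abuse-related TEAEs are identified by the protocol's method: a text-string search for indications of abuse potential across every preferred term, every verbatim term and every open text field in the AE data. Use the result for CT-8.8.1, CT-8.8.2 and CT-9.5.

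Preferably, append the search strings and fix them, together with the rule for reviewing hits, before unblinding. This is an addition to good order; Protocol Section 8.8.6 does not ask for it.

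If the sponsor intends the narrower search, declare and justify it in SAP Section 15 and attach the list of preferred terms.

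The cost is one SAP sentence, a short list, and a text search of AE data already collected in about 126 subjects. The one drawback is some false-positive hits to review.
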